1.2. Study Objectives

1.2.1. Primary Objective

The primary objective of study R668-AD-2217 is to describe further the efficacy of dupilumab on the extent and severity of eczematous lesions in skin of color participants, ≥ 12 years old with moderate-to-severe AD.

1.2.2. Secondary Objectives

The secondary objectives of the study are:

- To describe further the efficacy of dupilumab on pruritus and other AD symptoms in skin of color participants ≥ 12 years old with moderate-to-severe AD
- To describe further the efficacy of dupilumab on measures of mental health (anxiety and depression) and QOL in skin of color participants ≥ 12 years old with moderate- to-severe AD
- To describe further the safety of dupilumab administered to skin of color participants ≥ 12 years old with moderate-to-severe AD
- To assess further dupilumab modulation of type 2 biomarkers in skin of color participants ≥ 12 years old, with moderate-to-severe AD

- To evaluate further the systemic exposure of dupilumab in skin of color participants ≥ 12 years old with moderate-to-severe AD

1.2.3. Exploratory Objectives

The exploratory objectives of the study are:

- To describe and photograph clinical phenotypes of moderate-to-severe AD in skin of color participants, ≥ 12 years old and associated dupilumab treatment responses
- To assess erythema and pigmentation changes related to moderate-to-severe AD in skin of color participants ≥ 12 years old through clinical assessments, patient-reported severity and impact, and direct colorimetric measurement in AD lesional, hyperpigmentation lesional, and non-lesional skin
- To assess skin dryness changes in moderate-to-severe AD in skin of color participants ≥ 12 years old through clinical assessment of dryness and patient-reported severity and impact
- To assess pre and post dupilumab structural changes in skin of color AD lesional, hyperpigmentation lesional, and non-lesional skin via Optical Coherence Tomography (OCT) with possible additional non-invasive imaging at the discretion of the investigator (including line field confocal OCT and/or reflectance confocal microscopy)
- To study dupilumab mechanism of action (related to efficacy and/or safety), the biology of IL-4R, IL-4, IL-13, and related pathways, AD, and related diseases.

1.2.4. Revision History for SAP Amendments

None.

2. STUDY DESIGN

2.1. Study Description and Duration

This is a phase 4 US-only multicenter open-label monotherapy study to describe further the efficacy and safety of dupilumab treatment for 24 weeks, with dosing per USPI in adolescent and adult (≥ 12 years old) skin of color participants with moderate-to-severe AD.

2.2. Sample Size

Due to the descriptive character of this study, no formal sample size calculation was performed. The sample size of this study was chosen empirically to support descriptive analysis of efficacy and safety in the overall skin of color population and the Fitzpatrick skin type subgroups (FST 4, 5, and 6).

[figure not shown]
Up to 120 participants will be enrolled at approximately 30 US sites.

2.3. Study Plan

The study consists of a screening period and a treatment period.

The study flow diagram is described in [Figure 1](#).

Figure 1: Study Flow Diagram

* Preceded by loading dose

^p V3 at day 8 will be conducted as a phone visit

The Schedule of Events table is presented in [Appendix 10.2](#).

3. ANALYSIS POPULATIONS

In accordance with guidance from the International Conference of Harmonization of Technical Requirements for Registration of Pharmaceuticals for Human Use (ICH) guideline ICH E9 Statistical Principles for Clinical Trials (1998), the following populations will be used for all statistical analyses:

3.1. Full Analysis Set (FAS)

The full analysis set (FAS) includes all participants who are enrolled in the study and have baseline assessment. The FAS is the main analysis population for the study and will be used to summarize patient disposition, baseline characteristics and to analyze efficacy variables.

3.2. The Safety Analysis Set (SAF)

The safety analysis set (SAF) includes all participants in the FAS who are enrolled and received at least 1 dose of dupilumab during the study. Treatment administration, compliance and all safety variables will be analyzed using the SAF.

3.3. Pharmacokinetic Analysis Set

The PK analysis population includes all participants who received any study drug and who had at least 1 non-missing PK result.

4. ANALYSIS VARIABLES

4.1. Demographic and Baseline Characteristics in Study

The following demographic and baseline characteristics variables in the study will be summarized:

- Demographic variables:
 - Age (year)
 - Age group (≥ 12 - < 18 years, ≥ 18 - < 40 years, ≥ 40 - < 65 years, ≥ 65 years)
 - Sex (Male, Female)
 - Standard Race Categories: White, Black or African American, Asian, American Indian or Alaska Native, Native Hawaiian or Other Pacific Islander, Other
 - Expanded Race Categories
 - Ethnicity (Hispanic or Latino, Not Hispanic or Latino)
 - Baseline Weight (kg)
 - Baseline Weight with grouping (for adolescents ages ≥ 12 to < 18 years: < 60 kg, ≥ 60 kg; for adults ≥ 18 years: < 60 kg, ≥ 60 - < 90 kg, ≥ 90 kg)
 - Baseline Height (cm)
 - BMI (kg/m^2)
 - BMI with grouping (< 35 , ≥ 35 - < 40 , ≥ 40)
- Baseline characteristics:
 - Fitzpatrick Skin Type total score
 - Fitzpatrick Skin Type category
 - Duration of AD
 - Investigator's Global Assessment (IGA)
 - Eczema Area and Severity Index (EASI)
 - SCORing Atopic Dermatitis (SCORAD)
 - Body surface area (BSA) affected by AD
 - Patient Global Impression of Disease (PGID)
 - Patient Global Impression of Change (PGIC)
 - Patient Oriented Eczema Measure (POEM)
 - Dermatology Life Quality Index (DLQI) in patients ≥ 16 years of age
 - Children's Dermatology Life Quality Index (CDLQI) in patients < 16 years of age
 - Peak Pruritus Numerical Rating Scale (NRS) – weekly average at baseline

- Skin Pain NRS
- Sleep Quality NRS
- Hospital Anxiety and Depression Scale (HADS)
- AD Phenotypic Description
- Post Inflammatory Hyperpigmentation Severity Scale (PHSS)
- Dyspigmentation NRS
- Xerosis NRS

4.2. Medical History

Medical history will be coded to a Preferred Term (PT), high level term (HLT) and associated primary System Organ Class (SOC) according to the latest available version of Medical Dictionary for Regulatory Activities (MedDRA) at the coding CRO.

4.3. Pre-treatment / Concomitant Medications and Procedures

Medications/Procedures will be recorded from the day of informed consent until the end of study (EOS) visit. Medications will be coded to the Anatomical Therapeutic Chemical (ATC) level 2 (therapeutic main group) and ATC level 4 (chemical/therapeutic subgroup), according to the latest available version of WHO Drug Dictionary (WHODD) at the coding CRO. Patients will be counted once in all ATC categories linked to the medication.

Pre-treatment medications/procedures: medications taken, or procedures performed prior to administration of the first study drug.

Concomitant medications/procedures: medications taken, or procedures performed following the first dose of study drug of current study through the EOS visit.

4.4. Efficacy Data

4.4.1. Primary Efficacy Data

The primary endpoint in the study is:

EASI-75 (percent of patients achieving $\geq 75\%$ reduction from baseline in EASI) at week 24

4.4.2. Secondary Efficacy Data

Secondary efficacy endpoints in this study are:

Investigator Assessed Endpoints:

- Investigator's Global Assessment (IGA)
- Eczema Area and Severity Index (EASI)

EASI-50 ($\geq 50\%$ reduction from baseline in EASI)

- EASI-75 ($\geq 75\%$ reduction from baseline in EASI)
- EASI-90 ($\geq 90\%$ reduction from baseline in EASI)
- SCORing Atopic Dermatitis (SCORAD)
- Body surface area (BSA) affected by AD
- Post Inflammatory Hyperpigmentation Severity Scale (PHSS)
- AD Phenotypic Description

Patient Reported Outcome:

- Peak Pruritus (PP) NRS
- Sleep Quality NRS
- Skin Pain NRS
- Dermatology Life Quality Index (DLQI; age ≥ 16)
- Children's Dermatology Life Quality Index (CDLQI; age < 16)
- Patient Oriented Eczema Measure (POEM)
- Hospital Anxiety and Depression Scale (HADS) total score, anxiety and depression sub-scores
- Patient Global Impression of Disease (PGID)
- Patient Global Impression of Change (PGIC)
- Dyspigmentation NRS
- Xerosis NRS

Detailed description of the efficacy endpoints are described in Appendix Section 10.3

4.4.3. Other Efficacy Data

Other efficacy data include:

- Photography (select sites)
- Optical Coherence Tomography and non-invasive in vivo imaging (single site)
- Colorimetry measurement sub-study (at selected sites)

4.5. Safety Data

4.5.1. Adverse Events and Serious Adverse Events Variables

Adverse events and SAEs will be collected from the time of informed consent signature and then at each visit until the end of the study. All AEs are to be coded to PT, HLT and associated SOC according to the latest available version of MedDRA at the coding CRO.

An AE is any untoward medical occurrence in a patient administered a study drug which may or may not have a causal relationship with the study drug. Therefore, an AE is any unfavorable and unintended sign (including abnormal laboratory finding), symptom, or disease which is temporally associated with the use of a study drug, whether or not considered related to the study drug.

AEs also include: any worsening (i.e., any clinically significant change in frequency and/or intensity) of a pre-existing condition that is temporally associated with the use of the study drug; abnormal laboratory findings considered by the investigator to be clinically significant; and any untoward medical occurrence.

A SAE is any untoward medical occurrence that at any dose results in death; is life-threatening; requires in-patient hospitalization or prolongation of existing hospitalization; results in persistent or significant disability/ incapacity; is a congenital anomaly/ birth defect; or is an important medical event.

The criteria for determining whether an abnormal laboratory, vital sign or electrocardiogram (ECG) finding should be reported as an AE are as follows:

- Test result is associated with accompanying symptoms, and/or
- Test result requires additional diagnostic testing or medical/surgical intervention, and/or
- Test result leads to a change in dosing (outside of protocol-stipulated dose adjustments) or discontinuation from the study, significant additional concomitant drug treatment, or other therapy

The pre-treatment period is defined as the period from the subject providing informed consent up to the first dose of study drug in current study.

The treatment period is the period starting from the first dose date up to the last dose date + 7 days.

The follow-up period is the period starting 1 day after end of treatment (EOT) period up to the EOS visit.

The overall study period consists of treatment and follow-up period.

The pre-treatment AE and TEAE are defined as following:

- Pre-treatment signs and symptoms (Pre-treatment AEs) are AEs that developed or worsened in severity during pre-treatment period.
- Treatment-emergent adverse events (TEAEs) are defined as AEs with either initial onset after the first study intervention or that worsen after the first study intervention.
- Adverse event of special interest (AESI) includes these events below as listed in eCRF:

Anaphylactic reactions

Systemic hypersensitivity reactions

Helminthic infections

Any severe type of conjunctivitis or blepharitis

Keratitis
Clinically symptomatic eosinophilia

4.5.2. Physical Examination Variables

The physical examination variable values are dichotomized to normal and abnormal.

A thorough and complete physical examination will be according to the time points in Section 10.2.

4.5.3. Laboratory Safety Variables

Pregnancy testing will be performed for all female patients of childbearing potential at time points according to Section 10.2.

4.5.4. Vital Sign Variables

N/A

4.6. Biomarker Variables

Biomarkers Endpoint for this study is:

- Change and percentage change in total and allergen-specific IgE from baseline to weeks 4, 12 and 24

Total serum IgE and allergen-specific IgE are markers of Th2 activity and are downstream of IL-4/13 signaling. These analytes will be assessed as measures of Th2 activity and pharmacodynamic effect of the drug.

Patients with total serum IgE levels in the normal range may still have antigen-specific IgE in circulation, indicating they are atopic. To further understand atopy in this patient population, region-specific, allergen-specific IgE panels will be performed.

Samples will be collected at time points according to the schedule in Section 10.2.

5. GENERAL STATISTICAL ANALYSIS METHODS

For continuous variables, descriptive statistics will include the following: the number of patients reflected in the calculation (n), mean, median, Q1 (25% percentile), Q3 (75% percentile), standard deviation (SD), minimum, and maximum. For categorical or ordinal data, percentages will be displayed for each category.

5.1. Subject Disposition

The following summaries by table will be provided for all patients in FAS:

- The total number of screened patients
- The total number of enrolled patients
- The total number of patients in each analysis set
- The total number of patients who discontinued the study and the reasons for discontinuation
- The total number of patients who discontinued the study treatment and the reasons for discontinuation

5.2. Demographics and Baseline Characteristics

The following demographics and baseline characteristics as specified in Section 4.1 will be summarized for all patients in FAS.

- Demographics
- Baseline characteristics

5.3. Medical History

Medical history will be summarized by primary SOC and PT. The table will be sorted by decreasing frequency of SOC, HLT followed by PT. Medical history will be displayed on FAS.

5.4. Pre-treatment/Concomitant Medications and Procedures

Prohibited medications/procedures and rescue medications/procedures will be adjudicated from all medication/procedure collected. Number and percent of patients taking pre-treatment/concomitant medication, prohibited medications/procedures and rescue medications/procedures will be summarized, sorted by decreasing frequency of ATC Level 2 and ATC level 4. Patients will be counted only once for each medical class (ATC level 2 and 4) linked to the medication.

The procedure will be summarized by treatment group to the corresponding MedDRA by system organ class (SOC) and preferred term (PT) and sorted by decreasing frequency of SOC and PT.

Listing Prohibited medications/procedures and rescue medications/procedures will include generic name and ATC levels 2 and 4, indication, study day onset (for medications started before treatment, the study day onset =defined as date of medication start - date of the first dose; for medications started on or after treatment, the study day onset = date of medication start - date of the first

dose+1), the study end date (defined similarly as for study onset day), ongoing status, dose, frequency, route.

5.5. Dose administration

N/A

5.6. Treatment Exposure and Observation Period

The duration of treatment exposure period during the study is calculated as:

(Date of last study drug injection – date of first study drug injection) + 7

Exposure will be calculated based on the last study drug injection date and first study drug injection date regardless of temporary dosing interruption.

The duration of exposure will be summarized using number of patients, mean, SD, median, minimum and maximum.

In addition, the duration of exposure will be summarized categorically by patient counts and percentages for each of the following categories and cumulatively by these categories as well:

≥ 7 days, ≥ 14 days, ≥ 21 days, ≥ 28 days, ≥ 35 days, ≥ 42 days, ≥ 49 days, ≥ 56 days, ≥ 63 days, ≥ 70 days, ≥ 77 days, ≥ 84 days, ≥ 98 days, ≥ 112 days, ≥ 126 days, ≥ 140 days, ≥ 154 days.

The duration of observation period during the study in weeks is calculated as:

[(Date of the last visit – date of the first study medication dose) +1]/7.

The duration of observation period will be summarized descriptively as continues variable (n, mean, SD, median, minimum and maximum). In addition, the number and percentage of patients will be presented by specific time periods of interest as below:

≥ 8 days, ≥ 15 days, ≥ 22 days, ≥ 29 days, ≥ 36 days, ≥ 43 days, ≥ 50 days, ≥ 57 days, ≥ 64 days, ≥ 71 days, ≥ 78 days, ≥ 85 days, ≥ 99 days, ≥ 113 days, ≥ 127 days, ≥ 141 days, ≥ 155 days.

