Q2W SC injections of 200 mg dupilumab following a loading dose of 400 mg on day 1 for adolescents weighing ≥ 30 to < 60 kg. During the treatment period, participants will have a phone visit on week 1 and a clinic visit on week 2 and week 4, followed by monthly clinic visits through the end of treatment. Participants and/or parents/caregivers (as deemed appropriate based on age of participant), will be trained on injecting study drug at visit 2. Safety, laboratory, and clinical assessments will be performed at specified clinic visits, as noted in the Schedule of Events (SoE) [Table 1](#). The end of treatment period visit occurs at week 24, 2 weeks after the last dose of study drug.

In light of the public health emergency related to COVID-19, the continuity of clinical study conduct and oversight may require implementation of temporary or alternative mechanisms. Examples of such mechanisms may include, but are not limited to, any of the following: phone contact, virtual visits, telemedicine visits, online meetings, non-invasive remote monitoring devices, use of local clinic or laboratory locations, and home visits by skilled staff. Additionally, no waivers to deviate from protocol enrollment criteria due to COVID-19 will be granted. All temporary mechanisms utilized, and deviations from planned study procedures are to be documented as being related to COVID-19 and will remain in effect only for the duration of the public health emergency.

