8. STUDY TREATMENTS

8.1. Investigational Treatments

Dosing of dupilumab will be for 24 weeks and in accordance with the USPI. Participants will receive 1 of 2 dose regimens based on age and body weight:

For adults and for adolescents (weighing ≥ 60 kg): initial dose of 600 mg (2 x 300 mg injections), followed by 300 mg Q2W

Dupilumab drug product is supplied for this dose in the following concentration:

- Dupilumab 150 mg/mL: Each 2.25 mL single-use prefilled syringe with needle shield delivers 300 mg of study drug (2.0 mL of a 150 mg/mL solution)

For adolescents weighing ≥ 30 to < 60 kg: initial dose of 400 mg (2 x 200 mg injections), followed by 200 mg Q2W

Dupilumab drug product is supplied for this dose in the following concentration:

- Dupilumab 175 mg/mL: Each 1.14 mL single-use prefilled syringe with needle shield delivers 200 mg of study drug (1.14 mL of a 175 mg/mL solution)

Instructions on dose preparation are provided in the pharmacy manual. Subcutaneous (SC) injection sites should be alternated among the different quadrants of the abdomen (avoiding navel and waist areas), upper thighs, and optionally upper arms, so that the same site is not injected for 2 consecutive weeks. To allow for adequate assessment of possible ISRs, study drug should be administered only into areas of normal looking skin. Instructions for recording and reporting ISRs will be provided in the study reference manual.

Participants and/or parents/caregivers (as deemed appropriate based on age of participant), will be trained on injecting study drug at visit 2 and may self-inject study drug during weeks in which no clinic visit is scheduled.

Detailed instructions for transport, storage, preparation, and administration of study drug will be provided by the site to the participant (or caregiver). Participants and/or parents/caregivers will document/report compliance with self-injection of study drug in a diary.

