9.1.1. Footnotes for the Schedule of Events Table**9.1.1.1. Table 1 Schedule of Events**

1. In light of the public health emergency related to COVID-19, the continuity of clinical study conduct and oversight may require implementation of temporary or alternative mechanisms. Examples of such mechanisms may include, but are not limited to, any of the following: phone contact, virtual visits, telemedicine visits, online meetings, non-invasive remote monitoring devices, use of local clinic or laboratory locations, and home visits by skilled staff. Additionally, no waivers to deviate from protocol enrollment criteria due to COVID-19 will be granted. All temporary mechanisms utilized, and deviations from planned study procedures in response to COVID-19 are to be documented as being related to COVID-19 and will remain in effect only for the duration of the public health emergency.
2. The length of the screening period is not fixed but must not exceed 35 days.
3. All visit 10 assessments should be performed if a participant terminates the study after the baseline visit and prior to the visit 10 window (early termination visit).
4. Eligibility based on age and weight at time of screening visit.
5. Assent collected from participant, if applicable, based upon the age of the participant.
6. The questionnaires will be administered only to those participants who speak fluently the language(s) in which the questionnaire is presented (based on availability of validated translations). Patient-reported assessments are completed only by the participant.
7. Training of participants/parents/caregivers regarding completion of diary at visit 1 to record assessment of PP NRS and Sleep Quality NRS. Provide additional training as necessary based on review of diary use.
8. Dupilumab to be dosed as per USPI. Study drug administration will occur Q2W. Q2W study drug administrations must be separated by at least 11 days. At the baseline visit, study drug will be administered at the clinic and thereafter study medication will be provided to participants for administration at home. If the investigator and participants (\pm parent/guardians as appropriate) agree, participants may return to the clinic for dupilumab administration (as prescribed) instead.
9. Last scheduled dose of dupilumab during the treatment period will be at week 22.

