11.4.5.3. Treatment Exposure

The duration of exposure during the study will be presented by treatment group and calculated as:

Q2W dosing: (Date of last study drug injection – date of first study drug injection) + 14 days

The number (%) of participants exposed to study drug will be presented by specific time periods. The time periods of interest will be specified in the SAP.

In addition, duration of exposure during the study will be summarized using number of participants, means, standard deviation, minimums, medians, and maximums.

A summary of the number of doses will be provided.

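### The SAP adds 7 days to the injection interval where the protocol adds 14, so every treated participant's exposure is reported one week short

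*SAP*

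**What the plan says.** Protocol section 11.4.5.3 gives the exposure formula as "Q2W dosing: (Date of last study drug injection – date of first study drug injection) + 14 days". On what remains open, it says "The time periods of interest will be specified in the SAP".

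SAP section 5.6 gives the formula as "Date of last study drug injection – date of first study drug injection) + 7", applied regardless of temporary dosing interruptions. It then lists cumulative categories every 7 days from at least 7 to at least 84 days, followed by 98, 112, 126, 140 and 154 days. No reason is given for the different constant, and the SAP's revision history is empty.

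The dosing schedule comes from the protocol:

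- Section 8.1: "Dosing of dupilumab will be for 24 weeks and in accordance with the USPI".
- Section 9.1.1.1, footnotes 8 and 9: "Study drug administration will occur Q2W" and "Last scheduled dose of dupilumab during the treatment period will be at week 22".
- Section 6.1: "The end of treatment period visit occurs at week 24, 2 weeks after the last dose of study drug".

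SAP section 4.5.1 also ends its treatment period 7 days after the last dose and places the remaining time up to the end-of-study visit in a follow-up period. It adds that "The overall study period consists of treatment and follow-up period".

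**The concern.** Two current texts define one quantity in two ways, and only one of the definitions fits the dosing schedule. The constant added after the last injection stands for the time that injection is meant to cover. Under two-weekly dosing that is 14 days. No regimen in this trial has a 7-day interval.

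If the SAP is programmed as written, the report will show participants who took every dose on time as having 23 weeks of exposure in a study planned for 24. The duration summaries and part of the category table will not follow the protocol's definition. All analyses in this study are descriptive, so the exposure table is a result in its own right.

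**Working it through.** **Inputs.** Doses are two weeks apart, and the last is scheduled at week 22, which is 22 × 7 = 154 days after day 1. Planned treatment is 24 × 7 = 168 days. Let d be the last injection date minus the first, in days. Protocol exposure is d + 14 and SAP exposure is d + 7.

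**Reproducing the planned duration.**

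- Protocol: 154 + 14 = 168 days = 24.0 weeks, as planned.
- SAP: 154 + 7 = 161 days = 23.0 weeks.

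**Size of the difference.** (d + 14) − (d + 7) = 7 days for every d. As a share of the protocol value:

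- full course: 7/168 = 4.2%
- last dose at week 12 (d = 84): 91 against 98 days, 7/98 = 7.1%
- single dose (d = 0): 7 against 14 days, 7/14 = 50%

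A constant shift moves the mean, median, minimum and maximum by 7 days and leaves the SD unchanged.

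**Highest SAP category reached, last dose exactly on schedule.**

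| Last dose (week) | SAP days | SAP category | Protocol days | Protocol category |
|---|---|---|---|---|
| 0 | 7 | ≥7 | 14 | ≥14 |
| 2 | 21 | ≥21 | 28 | ≥28 |
| 4 | 35 | ≥35 | 42 | ≥42 |
| 6 | 49 | ≥49 | 56 | ≥56 |
| 8 | 63 | ≥63 | 70 | ≥70 |
| 10 | 77 | ≥77 | 84 | ≥84 |
| 12 | 91 | ≥84 | 98 | ≥98 |
| 14 | 105 | ≥98 | 112 | ≥112 |
| 16 | 119 | ≥112 | 126 | ≥126 |
| 18 | 133 | ≥126 | 140 | ≥140 |
| 20 | 147 | ≥140 | 154 | ≥154 |
| 22 | 161 | ≥154 | 168 | ≥154 |

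Eleven of the 12 on-schedule stopping points fall one category lower under the SAP. The full course does not.

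**Off-schedule dates.** These counts are of possible values of d, not of participants.

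- d = 0 to 76: all 77 values fall one category lower. Footnote 8 requires at least 11 days between doses, so d = 1 to 10 should not occur. That leaves 77 − 10 = 67 permitted values, all of which shift.
- d = 77 to 146, where cut-points are 14 days apart: 35 of 70 values shift (84–90, 98–104, 112–118, 126–132, 140–146). For example, d = 97 gives 104 and 111 days, both in ≥98, so there is no shift.
- d ≥ 147: none shift. A week-22 last dose changes category only if given at least 8 days early (d = 146: 153 against 160 days).

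The two formulas never differ by more than one category.

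**Other outputs.**

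- The SAP defines treatment-emergent events by onset or worsening after first study treatment, with no upper time limit, so their counts do not change.
- Compliance (Protocol 11.4.5.4) counts injections within the exposure period. With the last injection on study day d + 1, that period ends on day d + 7 or d + 14, and the next planned dose is on day d + 15. On exact dates the planned count is therefore the same under both formulas.

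**The case against.** The strongest reply is that 7 days looks like a convention and not a slip. SAP 4.5.1 uses it too, and the ≥7-day category is exactly the single-dose value under it. The protocol's statistical section also carries template residue, such as summaries by treatment group in a single-arm study, so its formula need not be treated as beyond question. This shows that the SAP is consistent with itself. It does not explain the departure from the protocol or make 7 days fit two-weekly dosing. It does mean that SAP 4.5.1 has to be reconciled along with 5.6. Otherwise exposure would run 7 days past the SAP's own treatment period.

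A second reply is that few participants change category. The protocol allows for up to 15% dropout, and 0.15 × 120 = 18. If dropouts are taken as the early stoppers, about 18 people could be affected, some of whom would not shift. That is fair for the category table. The 7-day offset in the duration statistics still applies to everyone treated.

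A third is that the reach could be wider than the exposure tables. The LOCF-NRI sensitivity analysis in SAP 5.7.1 depends on completing at least 16 weeks of treatment, which the SAP does not define. If that were derived from exposure, a last dose at week 14 would give 98 + 14 = 112 days (16 weeks) under the protocol but 98 + 7 = 105 days (15 weeks) under the SAP. This is conditional, but it is a reason to settle the definition.

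**Conclusion.** The concern holds. The SAP constant conflicts with the protocol without explanation and does not reproduce the planned 24 weeks. Reported exposure is 7 days short for every treated participant, and a nominal full course appears as 161 days instead of 168. The 7-day difference needs no assumption beyond the two printed formulas. Treating 14 as the fitting constant rests on the two-weekly schedule, the week-22 last dose and the week-24 end of treatment, all stated in the protocol.

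The established consequence is confined to descriptive exposure summaries. The primary analysis is unaffected, as are counts of treatment-emergent events. The point is worth correcting because the error is certain and cheap to remove, but it does not threaten the study's conclusions.

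**What to change.** - Change the constant in SAP 5.6 from 7 to 14, matching Protocol 11.4.5.3.
- In the same edit, reconcile the end of the treatment period in SAP 4.5.1 with the protocol, or state why it differs. Keep the follow-up period, since it carries events after the treatment period through to the end-of-study visit.
- Optionally, add a ≥161-day category. Under the corrected formula a nominal week-20 last dose (154 days) and a full course (168 days) both fall in ≥154. The extra row separates them on nominal dates: a full course ending 7 days early gives 161 days (in), and a week-20 dose 6 days late gives 160 days (out). It does not separate them completely, because a week-20 dose 7 days late also gives 147 + 14 = 161 days.

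The cost is one constant in the SAP and in the exposure program, a check of the wording in SAP 4.5.1, and at most one table row. There is a small drawback. With 14 added, nominal last doses at weeks 12 to 20 land exactly on cut-points, so a dose one day early drops a category, whereas adding 7 leaves a 7-day margin. Last doses at weeks 2 to 10 sit on a cut-point under either formula. The ≥7-day row becomes redundant but does no harm.
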